### **7.1. Adverse Events and Deaths**

#### **7.1.1. Adverse Event Dictionary**

Clinical and laboratory AEs will be coded using the current version of the Medical Dictionary for Regulatory Activities (MedDRA). System organ class (SOC), high-level group term, high-level term (HLT), preferred term (PT), and lower-level term will be provided in the AE dataset.

#### **7.1.2. Adverse Event Severity**

Adverse events are graded by the investigator as Grade 1, 2, 3, 4, or 5 according to toxicity criteria specified in the protocol. The severity grade of events for which the investigator did not record severity will be categorized as “missing” for tabular summaries and data listings. The missing category will be listed last in summary presentation.

#### **7.1.3. Relationship of Adverse Events to Study Drug**

Related AEs are those for which the investigator selected “Related” on the AE eCRF to the question of “Related to Study Treatment.” Relatedness will always represent the investigator’s choice, not that of the medical monitor. Events for which the investigator did not record relationship to study drug will be considered related to study drug for summary purposes. However, by-participant data listings will show the relationship as missing.

#### **7.1.4. Serious Adverse Events**

Serious adverse events (SAEs) will be identified and captured as SAEs if the AEs met the definitions of SAEs that were specified in the study protocol. SAEs captured and stored in the clinical database will be reconciled with the SAE database from the Global Patient Safety (formerly known as Pharmacovigilance and Epidemiology) before data finalization.

#### **7.1.5. Treatment-Emergent Adverse Events**

##### **7.1.5.1. Definition of Treatment-Emergent Adverse Events**

The TEAEs are defined as any AEs that begin on or after the date of first dose of study drug or any AEs leading to premature discontinuation of study drug. For participants who discontinue from the oral bridging of LEN, only AEs collected up to 60 days after the Last Dose Date of Oral Bridging will be considered treatment emergent.

#### 7.1.5.2. Incomplete Dates

If the onset date of the AE is incomplete and the AE stop date is not prior to the first dose date of study drug, then the month and year (or year alone if month is not recorded) of onset determine whether an AE is treatment emergent. The event is considered treatment emergent if the AE onset is the same as or after the month and year (or year) of the first dose date of study drug.

An AE with completely missing onset and stop dates, or with the onset date missing and a stop date later than the first dose date of study drug, will be treatment emergent. In addition, an AE with the onset date missing and incomplete stop date with the same or later month and year (or year alone if month is not recorded) as the first dose date of study drug will be considered treatment emergent.

When calculating the duration of event or time to onset, the following imputation rule will be used:

Missing start month/day: Jan 1/first day of the month will be used unless this is before the start date of study drug; in this case the study drug start date will be used;

Missing stop month/day: Dec 31/last day of the month will be used, unless this is after the last study date; in this case the last study date will be used.

Completely missing start or end dates will remain missing, with no imputation applied.

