### 3.8. Analysis Visit Windows

#### 3.8.1. Definition of Key Dates and Study Day

**First Dose Date** for All LEN Analysis is defined as the earliest dose date of either blinded or open-label oral LEN, as recorded on the Study Drug Administration eCRF form.

**Last Dose Date** for All LEN Analysis is defined for participants who prematurely discontinue study drug in any phase (ie, main phase or extension phase) of the study or who complete study drug as the latest dose date of either blinded or open-label oral LEN or SC LEN.

**First Dose Date** for the study is defined as the day when the first dose of blinded study drug (LEN or Placebo) or open-label oral LEN was taken, as recorded on the Study Drug Administration eCRF form.

**Last Dose Date** for the study is defined for participants who prematurely discontinue study drug in any phase of the study or who complete study drug as the latest dose date of any study drug including blinded study drug, open-label oral LEN, and SC LEN.

**First Dose Date of Oral Bridging** is defined for participants who received oral bridging of LEN as the earliest dose date of oral bridging of LEN, as recorded on the Study Drug Administration - Oral Bridging eCRF form.

**Last Dose Date of Oral Bridging** is defined for participants who received oral bridging of LEN, as the latest dose date of oral bridging of LEN before the First Dose Date of Resumed SC Injection, as recorded on the Study Drug Administration - Oral Bridging eCRF form.

**First Dose Date of Resumed SC Injection** is defined for participants who received oral bridging of LEN and resumed the SC injection, as the earliest dose date of SC LEN following the lifting of the Clinical Hold on SC LEN, as recorded on the Study Drug Administration – SC eCRF form.

**Last Study Date** is defined as the latest date of non-missing clinic visits and/or laboratory visits, and/or AE onset and end dates without any imputation, including the 30, 90, and 180-day follow-up visit dates for participants who prematurely discontinue or complete the study.

**Study Day** will be calculated from the First Dose Date, as defined separately above for All LEN Analysis and for the study, and will be derived as follows:

- For postdose study days: Assessment Date – First Dose Date + 1
- For study days prior to the first dose: Assessment Date – First Dose Date

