#### **7.1.7. Additional Analysis of Adverse Events**

##### **7.1.7.1. Study Drug Related Injection Site Reactions**

Additional analysis of AEs will be performed for injection site reaction (ISR) related to study drug, which is defined as an AE related to study drug with HLT of “Injection Site Reactions”. The following summaries will be provided for each SC injection (eg, Day 1 SC, Week 26, and Week 52) and the overall using All LEN Analysis.

- Number of participants that received SC injection
- Number and percentage of participants with study drug related ISRs
- Number and percentage of participants with study drug related ISRs by grade
- Number and percentage of participants with study drug related ISRs by PT term

The denominator for the percentage calculation for the by visit summary and the overall summary will be based on the total number of participants who receive at least 1 SC injection at the visit of interest and the total number of participants who receive at least 1 SC injection at any injection visit, respectively.

Duration of the ISR will also be calculated and summarized. Duration for a given event is defined as the ISR stop date minus the ISR onset date plus 1 day. For ISR with ongoing stop date, stop date will be imputed as last study date or data cut date, whichever is the earliest. Duration of ISR events in days will be summarized using descriptive statistics.

A by-participant listing for study drug related ISRs and the corresponding duration will be provided.

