1. RTV is not considered as an ARV when used as a boosting agent, defined as RTV used as 100 mg QD or BID or as 200 mg QD or BID.
2. COBI is not an ARV.

4) Study drug administration: Oral reload will be recorded as an “Unscheduled” visit in the Study Drug Administration eCRF. participants with oral reload prior to the 1st dose of SC have “Unscheduled” dosing visits occurred prior to Day 1 SC visit. Participants who received a total of 5 tablets of LEN (300 mg) (ie, 2 x 300 mg LEN tablets each for the first 2 days and 1 x 300 mg LEN tablet on the 8th day) prior to “Unscheduled” dosing visits followed by Day 1 SC visit will be classified as oral reload due to missing scheduled SC dosing. Otherwise, participants will be classified as oral reload due to missing scheduled oral dosing visit.

5) GSS, PSS, and OSS calculation for the baseline OBR:

For participants enrolled based on historical genotypic reports, only GSS data for individual drugs are available, and the OSS is the same as the GSS. For participants enrolled based on the Screening report, GSS, PSS, and OSS data for individual drugs are provided in the Screening report. On occasions, drug scores for some participants combined scores from both historical report and Screening report. GSS, PSS, and OSS for the failing regimen and baseline OBR are calculated by summing up the scores from individual drugs in the regimens. GSS, PSS, and OSS data are stored in the Virology Database (GVD, Gilead Virology Database).

6) ARV definitions:

- a) Prior ARV: For an ARV with ARV.CMSCAT = “Prior ARV”, if the end date of the ARV is missing and not marked as ongoing, the ARV is considered ended prior to the 1st dose date.

7) Injection site reaction:

- a) To summarize ISRs by injection visit, each study drug related ISR will be associated with one injection visit (eg, Day 1 SC injection, Week 26 SC Injection, Week 52 SC injection) based on the start date of the ISR. If the start date of the ISR is on or after a given injection visit date and prior to the next injection visit date, if available, the ISR will be associated with that injection visit.
- b) For ISR summarized by PT:
  - i) For the overall summary (ie, participants received at least one injection), multiple ISRs with the same PT will only be counted once per participant for each PT.

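### A partly missing onset date for an injection site reaction can be imputed to before the injection, lengthening its duration, and the SAP does not say how such a reaction is linked to an injection

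*SAP*

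**What the plan says.** SAP 7.1.5.2 gives one rule for all adverse events. With only the day of onset missing, the "first day of the month will be used unless this is before the start date of study drug". With the month missing too, 1 January takes its place under the same limit. Where the limit applies, onset moves to the first dose instead. The rule opens by restricting its own scope: "When calculating the duration of event or time to onset, the following imputation rule will be used". Partial stop dates go the other way, to the end of the month or year, capped at the last study date.

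The section does not say which start date it means. SAP 3.8.1 defines two. For the All LEN Analysis the first dose date "is defined as the earliest dose date of either blinded or open-label oral LEN". For the study as a whole it is "the day when the first dose of blinded study drug (LEN or Placebo) or open-label oral LEN was taken". Both are oral doses. SAP 1.2 places the first injection (Day 1 SC) 14 days after the first oral LEN dose.

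For ISRs, SAP 7.1.7.1 states: "Duration for a given event is defined as the ISR stop date minus the ISR onset date plus 1 day". It has its own rule for an ongoing stop date but none for a partial onset. SAP 7.1.7.2 also summarises the duration of resolved events. SAP Appendix 3 item 7a says that "each study drug related ISR will be associated with one injection visit", using the start date of the ISR, and does not mention partial dates.

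**The concern.** A reaction at an injection site that is related to study drug cannot begin before an injection. The general rule does not use that fact. Near the first injection its floor is an oral dose two weeks too early. At Week 26 and later the floor lies far in the past and has no effect, so nothing stops the imputed onset from falling before the injection.

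ISR duration describes how well the subcutaneous product is tolerated, and the error is one-sided: moving onset to the start of the month can lengthen a duration but never shorten it. A partial stop date moved to month end would add to it. The by-injection summaries in SAP 7.1.7.1 and 7.1.7.2 also need each ISR tied to one injection, and for a partly dated ISR the programmer has no written rule.

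**Working it through.** The SAP gives no figure on this point, so there is nothing to reproduce. The check applies its date rules directly.

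**Inputs from the documents:** the imputation rule and floor (SAP 7.1.5.2); 14 days from first oral LEN to first injection (SAP 1.2); 28 days from first placebo dose to first injection in Cohort 1B (14 + 14); 182 days between injections (SAP 4.2); duration = stop − onset + 1 (SAP 7.1.7.1).

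**Assumptions, not in the documents:** the lag L from injection to true onset, and injection dates spread evenly over the calendar.

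**Share of cases dated before the injection, day missing.** In a 30-day month, the imputed onset precedes the injection when the injection is on day 2 or later and onset falls in the same month, that is, on injection days 2 to 30 − L. The share is (29 − L)/30, or zero if that is negative. The last column runs every date in a four-year calendar cycle (1461 dates).

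| Lag L (days) | (29 − L)/30 | Calendar |
|---|---|---|
| 0 | 29/30 = 96.7% | 96.7% |
| 1 | 28/30 = 93.3% | 93.4% |
| 3 | 26/30 = 86.7% | 86.9% |
| 7 | 22/30 = 73.3% | 73.7% |
| 14 | 15/30 = 50.0% | 50.7% |
| 30 | 0 | 0% |

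**Days added, later injections.** If onset falls on day d of the month, the rule adds d − 1 days. The mean is (0 + 1 + … + 29)/30 = 14.5 days, maximum 29. On the calendar it is 14.7, maximum 30.

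**Days added, first injection, floor at first oral LEN.** At lag 0 the addition is the smaller of d − 1 and 14. The mean is [(0 + 1 + … + 14) + 15 × 14]/30 = (105 + 210)/30 = 10.5 days (calendar 10.6), maximum 14. With a longer lag, the imputed onset is still at most 14 days before the injection, and the lag itself is added: the maximum is 17 days at lag 3. If the floor were the Cohort 1B placebo start, the lag-0 figures would be 14.7 on average and 28 at most.

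**Worked example.** Injection 20 June, true onset 21 June, stop 26 June, onset recorded as June only.

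- True duration: 26 − 21 + 1 = 6 days.
- SAP rule, later injection: 26 − 1 + 1 = 26 days.
- SAP rule, first injection, first oral dose 6 June: 26 − 6 + 1 = 21 days.
- Onset set to the injection date: 26 − 20 + 1 = 7 days.

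**Year-only onset, later injection.** The rule adds 182 days on average and up to 365. Nothing in the documents suggests that such dates occur.

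**Linkage.** SAP 7.1.5.2 restricts imputation to duration and time to onset, and item 7a is silent on partial dates. If the imputed date were reused in item 7a, a day-missing reaction to a later injection that was dated before it would go to the previous injection. A Day 1 SC reaction dated before Day 1 SC would link to no injection.

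**The case against.** A reader might infer that reactions will be credited to the wrong injection. The documents do not support that: the imputation is confined to duration and time to onset, and item 7a does not call on it. What can be said is that the linkage rule is missing.

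A reader might also infer that almost every partly dated ISR is affected. That depends on a short lag. It does not hold when the injection falls on the first of the month, or when the recorded onset month is later than the injection month.

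Partial dates may be few. Participants receive an ISR worksheet and are told to measure and report reactions (Protocol 6.3.2), and the Year 2 and Year 3 analyses wait for query resolution (SAP 2.1.5, 2.1.6). Durations are only described, and a few long values barely move a median or quartile. Overall ISR incidence, grade and preferred-term counts do not use the imputed onset. All of this stands, and it limits the weight of the point.

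The strongest defence is that earliest onset with latest stop is a deliberately conservative convention for safety durations. It stands for adverse events in general. For an ISR caused by a given injection, however, the earliest possible onset is the injection date. Going further back adds time in which the reaction could not have existed.

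**Conclusion.** The point holds in a narrow form and is minor. Followed as written, SAP 7.1.5.2 can date a drug-related ISR before its injection when the day is missing and onset is in the injection month, and the duration is then too long. With an assumed lag of 0 to 3 days this affects about 87% to 97% of injection dates and adds about 14.5 days on average. At a 14-day lag the share is about 51%. The first-dose floor matters only around Day 1 SC, where it limits backdating to 14 days on the scheduled timing. This takes the floor as first oral LEN, the natural reading because ISR summaries belong to the All LEN Analysis.

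These are sizes per affected event. The number of partial onset dates is not given, so no bias in the reported summaries can be claimed or sized. Item 7a has a gap on partial dates; misassignment would follow only if the imputed date were reused there.

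**What to change.** Add a rule to SAP 7.1.5.2 for study-drug-related ISRs, and refer to it in Appendix 3 item 7a:

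- **Month and year recorded, day missing.** Impute onset as the earliest SC injection date in that month that is not after the ISR stop date. If there is none, use the first of the month.
- **Limits.** Never impute an onset before the first SC injection or after the stop date. If the recorded dates cannot satisfy both, query the record.
- **Year only.** Query it. If it stays unresolved, list the event and leave it out of the duration and by-injection summaries.
- **One date.** Use the same imputed date for duration and for linkage in item 7a.

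The stop-date check is needed. Without it, an onset recorded as June with a stop on 10 June and an injection on 20 June would get a duration of 10 − 20 + 1 = −9 days. With the rule, the remaining overstatement for a reaction to the injection in question is at most the true lag.

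The cost is a short SAP insertion and a few lines of programming; no endpoint or clinical procedure changes. There is one downside: a reaction to an earlier injection that began in the month of a new injection, but before it, could be moved to the new injection and its duration shortened. Listing the affected records would let a reader see any such case.

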#### 7.1.6. Summaries of Adverse Events and Deaths

Treatment-emergent AEs will be summarized based on the Safety Analysis Set.

##### 7.1.6.1. Summaries of AE Incidence

A brief, high-level summary of the number and percentage of participants who experienced at least 1 TEAE in the categories described below will be provided for All LEN Analysis. All deaths observed in the study will also be included in this summary.

The number and percentage of participants who experienced at least 1 TEAE will be provided and summarized by SOC and PT and by PT only, unless specified otherwise, for the following AE categories:

- TEAEs
- TEAEs (by severity)
- TEAEs with Grade 3 or higher (by severity)
- TEAEs with Grade 2 or higher
- TE treatment-related AEs (by severity)
- TE treatment-related AEs with Grade 3 or higher (by severity)
- TE treatment-related AEs with Grade 2 or higher

- TE SAEs
- TE treatment-related SAEs
- TEAEs leading to death (by SOC and PT only)
- TEAEs leading to premature discontinuation of study drug
- TEAEs leading to premature discontinuation of study

Multiple events will be counted only once per participant in each summary. For summaries by SOC and PT, AEs will be summarized and listed first in alphabetic order of SOC and then by PT in descending order of total frequency within each SOC. For summaries by PT, AEs will be summarized and listed by PT in descending order of total frequency. For summaries by severity grade, the most severe grade will be used for those AEs that occurred more than once in an individual participant during the study.

In addition, data listings will be provided for the following:

- All AEs
- All SAEs
- All Deaths
- All AEs with severity of Grade 3 or higher
- All AEs leading to discontinuation of study drug
- All AEs leading to discontinuation of study

For each listing, whether the event is treatment emergent will be indicated.

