3.4. Duration of Treatment

Participants will be treated for at least 54 weeks. Following completion of the Functional Monotherapy Period (Cohort 1) or the oral lead-in Period (Cohort 2), participants will continue with study visits at Day 1 SC, Weeks 4, 10, 16, 22, 26, 36, and 52.

At the Week 52 visit, participants will be given the option to attend visits at Week 62, 78, 88, 104, 114, 130 and will continue to alternate between every 10 weeks and every 16 weeks.

At Week 156 and thereafter, upon regulatory and/or institutional review board (IRB)/independent ethics committee (IEC) approval of the protocol and when participants have provided written informed consent of the most current IRB-approved consent form, participants will continue to receive study drug every 26 weeks, and continue to attend visits every 26 weeks (± 2 weeks). Participants will receive SC LEN every 6 months (26 weeks) ± 2 weeks from the last injection starting at the Week 156 visit, while continuing their OBR, until the product becomes accessible to participants through an access program, is commercially available, or until Gilead elects to discontinue the study in the country.

Participants who decide not to receive SC LEN at Week 156 and not to continue the study will complete the study at Week 156 visit. Participants who decide to discontinue SC LEN early and do not wish to continue to attend study visits through Week 156 visit or next scheduled SC dosing visit will return to the clinic for 30-day, 90-day and 180-day follow-up visits after early termination visit. The 180-day follow-up may be conducted via a phone call per the investigator's discretion.

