Text has been updated to add more information regarding timing of reporting of serious adverse events (SAEs) and initial SAE reporting to align with internal processes.	Section 7.3.2.1

Rationale for Key Changes Included in Amendment 5	Affected Sections
Section describing management of injection site reactions (ISRs) that are Grade 3 or higher, or persisting for more than 26 weeks has been removed. The additional assessments and extended monitoring criteria described in this section were added to assess the risk of ISRs in participants who were exposed to subcutaneous lenacapavir administered from borosilicate vial lots. This section is deleted as use of borosilicate vials has been discontinued and adequate safety data to assess the risk of ISRs has been collected from the study to date. Additionally, currently there are only 13 participants remaining on the study.	Section 7.6.4
The section describing the safety monitoring committee has been removed because it is no longer applicable to the study. There are no additional meetings planned for the safety monitoring committee.	Section 7.8
Text describing the availability of study results on ClinicalTrials.gov has been added to align with new International Council for Harmonisation (ICH) guidance.	Section 9.2.2
A new section describing data protection has been added to align with new ICH guidance.	Section 9.3.5
Recommendations for phone contact with participants after Week 156 to follow up on AEs has been added.	Appendix 2
Minor changes to correct typographic errors.	Throughout, as needed

Amendment 4 (18 January 2023)

Rationale for Key Changes Included in Amendment 4	Affected Sections
Long-term data collection were added to support that lenacapavir in combination with optimized background regimen at Weeks 104 and 156 (from the first subcutaneous [SC] dose of GS-6207) have sustained durable virologic responses, clinically meaningful improvement in CD4+, and was well tolerated in people living with human immunodeficiency virus with multidrug resistance and limited options. Secondary objectives and endpoints have been added to reflect this long-term data collection. To reflect the long-term data collection window, Year 2 and 3 analyses have been added to the Week 104 and 156 analysis window.	Synopsis, Study Design Schema, Sections 2, 3, 5.5, 8, 8.2.3, and 8.2.4

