### **3.4.2. Participant Subgroups for Safety Analyses**

Incidence of all treatment-emergent AEs (TEAEs) will be analyzed for the following participant subgroups using the Safety Analysis Set for All LEN Analysis

- Age (years): (a)  $< 50$  and (b)  $\geq 50$
- Sex: (a) male and (b) female
- Race: (a) black and (b) nonblack
- Region: (a) US and (b) Ex-US

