#### **4.3. Study Duration**

Due to long-acting feature of the study drug, study duration will be calculated for All LEN Analysis using the Safety Analysis set.

All LEN Analysis Study duration is calculated as the last study date minus the first dose date of LEN plus 1. For participants who are still on study at the time of the Year 2 or Year 3 interim analysis, the data cut date will be used to impute the last study day.

Study duration will be expressed in days and will be summarized using descriptive statistics and using the number and percentage of participants that stayed through the following applicable time periods: 1 day, 2 days, 8 days, 15 days, 43 days, 85 days, 127 days, 169 days, 197 days, etc.

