## **7.7. Participant Subgroup for Safety Endpoints**

Incidence of all treatment-emergent AEs will be repeated within each subgroup defined in Section 3.4.2 using the Safety Analysis set for All LEN Analysis. Due to small number of participants available in each subgroup, results will be descriptive. No formal statistical testing is planned.

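### The general TEAE tables, including US versus ex-US, give crude percentages over open-ended follow-up, so differences between groups or analysis years cannot be separated from observation time

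*SAP*

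**What the plan says.** **Measure.** SAP 7.1.6.1: "The number and percentage of participants who experienced at least 1 TEAE will be provided and summarized by SOC and PT". The counting rule is "Multiple events will be counted only once per participant in each summary". The measure is therefore a proportion of the Safety Analysis Set, whatever each participant's follow-up. Protocol 8.6.2 plans the same measure, and SAP 7.8 declares no change.

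**Subgroups.** SAP 3.4.2: "Incidence of all treatment-emergent AEs (TEAEs) will be analyzed for the following participant subgroups using the Safety Analysis Set". One of these is "Region: (a) US and (b) Ex-US". SAP 7.7 confirms it: "Incidence of all treatment-emergent AEs will be repeated within each subgroup defined in Section 3.4.2 using the Safety Analysis set for All LEN Analysis".

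**Time at risk.** SAP 7.1.5.1 counts any event from first dose onward. The only upper limit is 60 days after the last oral bridging dose, for participants who discontinue from bridging. The analysis windows in SAP Table 3-1 run to Week 208.

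**End of follow-up.** After Week 52 continuation is optional. The Protocol Synopsis (Duration of Treatment) and Protocol Appendix 2, footnote e, let continuing participants stay until LEN is available through an access program, "is commercially available, or until Gilead elects to discontinue the study in the country". Protocol 3.4 has the same words, but in its paragraph on dosing from Week 156. The SAP is based on Amendment 4; its Appendix 1, footnote e, has the access-program and country-closure conditions without commercial availability.

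**Follow-up summary.** SAP 4.3: "study duration will be calculated for All LEN Analysis using the Safety Analysis set". Under SAP section 3 the default columns are cohort and total, so duration by region is not called for. Protocol 8.6.1 only lists exposure.

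**Injection site reactions.** SAP 7.1.7.1 divides by participants injected at the visit of interest for the by-visit tables, and by anyone ever injected for the overall column.

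**The concern.** A crude percentage with at least one event rises with follow-up even when the underlying rate does not change. Here the stopping rule after Week 52 operates country by country, and region is one of the safety subgroups. A regional difference in the TEAE table could therefore reflect how long participants in each region were observed, and the reader of that table is given no follow-up for either column. The same holds for cohort columns if cohorts were followed for different lengths. Between the Year 2 and Year 3 analyses the cumulative percentage can only stay the same or rise.

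The SAP recognises early completers elsewhere. The Week 104 snapshot (6.2.1) and the Missing = Failure denominators (6.3.2) exclude participants who have no HIV-1 RNA result and completed the study before the window closed. The general TEAE tables have no counterpart: no person-time rate, no common cut-off and no time-to-event summary.

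Safety at Weeks 104 and 156 is a secondary objective, yet the overall percentage refers to no stated period. What is at stake is interpretation. The safety analysis is descriptive, so no error rate is affected, and the primary endpoint is untouched.

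**Working it through.** The documents give no adverse event rate and no follow-up by region, so there is no figure of the plan's own to reproduce on this point. Rates and exit shares below are assumptions; follow-up times come from the visit schedule.

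**Inputs**
- Follow-up from first oral LEN: the Week 52, 104, 156 and 208 visits plus 2 weeks of oral lead-in give 54, 106, 158 and 210 weeks. In years, t = weeks × 7 / 365.25, so 54 weeks = 1.035 and 158 weeks = 3.028.
- Constant first-event rate λ, the same in both groups: 5, 10, 20 or 50 per 100 participant-years (assumed).
- Group A: a share s of 25%, 50% or 75% leaves at 54 weeks and the rest stay to 158 weeks. Group B: all stay to 158 weeks (assumed).

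**Step 1: crude percentage.** P(t) = 1 − exp(−λt). At λ = 0.10, P(54 weeks) = 1 − exp(−0.1035) = 9.8% and P(158 weeks) = 1 − exp(−0.3028) = 26.1%.

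**Step 2: spurious gap.** Gap = P(158) − [s × P(54) + (1 − s) × P(158)] = s × [P(158) − P(54)]. At λ = 0.10 and s = 50%, group A shows 0.5 × 9.8 + 0.5 × 26.1 = 18.0% against 26.1% in group B, a gap of 8.1 points.

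Crude percentages are shown by week of follow-up. Gaps are in percentage points, from unrounded values.

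| Rate per 100 participant-years | 54 wk | 106 wk | 158 wk | 210 wk | Gap, s = 25% | s = 50% | s = 75% |
|---|---|---|---|---|---|---|---|
| 5 | 5.0 | 9.7 | 14.0 | 18.2 | 2.3 | 4.5 | 6.8 |
| 10 | 9.8 | 18.4 | 26.1 | 33.1 | 4.1 | 8.1 | 12.2 |
| 20 | 18.7 | 33.4 | 45.4 | 55.3 | 6.7 | 13.4 | 20.0 |
| 50 | 40.4 | 63.8 | 78.0 | 86.6 | 9.4 | 18.8 | 28.2 |

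**Step 3: Year 2 to Year 3.** Moving follow-up from 106 to 158 weeks raises the percentage from 18.4% to 26.1% at 10 per 100 participant-years, and from 33.4% to 45.4% at 20, with no change in rate.

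**Step 4: near-universal events.** At 100 per 100 participant-years the percentages are 64.5, 86.9, 95.2 and 98.2. From 106 to 158 weeks the rise is 95.2 − 86.9 = 8.3 points, against 78.0 − 63.8 = 14.2 at a rate of 50. An any-TEAE row may therefore move less than a row for moderately common events.

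**Step 5: person-time rate, constant hazard.** Expected time to first event or end of follow-up is P(t)/λ per participant, so first events divided by person-time equals λ whatever t is. In the 50% scenario both groups give 10.0 per 100 participant-years at λ = 0.10, and 20.0 at λ = 0.20.

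**Step 6: person-time rate, early hazard.** Assume a rate of 1.0 per year for 6 months and none afterwards. The crude figure is 1 − exp(−0.5) = 39% at both 1 and 3 years. Person-years per participant are 0.393 + 0.607 × 0.5 = 0.697 at 1 year and 0.393 + 0.607 × 2.5 = 1.910 at 3 years. The rates are 0.393/0.697 = 56 and 0.393/1.910 = 21 per 100 participant-years, so longer follow-up now looks safer.

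**The case against.** The strongest reply is that the plan is descriptive and already reports follow-up. SAP 4.3 summarizes study duration, including the percentage staying through successive time points. SAP 4.1 splits disposition into Main and Extension Phases. SAP 7.7 says subgroup results are descriptive because numbers are small. All participants in the All LEN Analysis receive LEN, and no formal regional safety comparison is planned. This limits the harm to interpretation, but it does not put follow-up beside the regional columns or give the percentages a stated period.

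Second, a person-time rate is not neutral. Step 6 shows that the bias reverses if events cluster early. That objection stands. It is the reason for a common Week 52 cut to lead the region and cohort comparison, with the rate as a supplement.

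Third, a reader might infer that every adverse event table is affected. That is too broad: the per-injection reaction tables condition on having received that injection and are largely free of the problem. Only their overall column shares it.

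Fourth, a reader might take the Amendment 5 remark that "currently there are only 13 participants remaining on the study" as evidence of uneven exit. Against 72 enrolled (Protocol 1.2.2.2), 72 − 13 = 59 had left by May 2024. The remark says nothing about their region, their reasons, or follow-up at the Year 2 or Year 3 cut.

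**Conclusion.** The point holds for the general TEAE tables, the region subgroup table and the overall injection site reaction column. They give crude percentages over open-ended follow-up, under an exit rule that can make follow-up differ by region or cohort and with follow-up that grows between analyses. As planned, a difference in these percentages cannot be separated from observation time.

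Two stronger readings are tempting and are not supported. One is that the regional comparison is confounded with follow-up by design. The exit rule makes that possible, but neither document gives follow-up by region, and ex-US pools several countries. Whether a difference exists, and which region it would make look worse, is unknown. The other is that the artefact reaches 19 to 38 points. That needs whole groups to stop at different times: at 0.3 per year, 25.9% after 1 year against 45.1% after 2; at 0.5 per year, 39.3% after 1 year against 77.7% after 3.

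With partial exit the gap is about 2 to 28 points. That range rests on assumed constant rates of 5 to 50 per 100 participant-years and assumed exit shares of 25% to 75% at 54 weeks. It is an illustration, not an estimate for this trial.

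**What to change.** 1. Keep the crude tables in SAP 7.1.6.1 and 7.7.
2. In SAP 7.7, base the region comparison on TEAEs in the Main Phase (to Week 52), where all participants follow one visit schedule. Do the same for comparisons between cohort columns.
3. In SAP 4.3, add study duration by region, so that follow-up can be read beside the subgroup table.
4. In SAP 7.1.6.1, add first events per 100 participant-years for all TEAEs, Grade 3 or higher, serious, treatment-related, and those leading to study drug discontinuation. Define time at risk as running from first LEN dose to the first event or the end of TEAE collection, including the 60-day limit after the last oral bridging dose where it applies.
5. Present that rate by Main and Extension Phase, or beside the Week 52 table, and state that it assumes a roughly constant hazard.

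**Cost.** A little more output. First-dose and last-study dates are already defined (SAP 3.8.1), and SAP 7.1.5.2 already has an imputation rule for time to onset. The time-at-risk rule is new and has to be written, because study duration in SAP 4.3 does not stop at the first event or at the 60-day limit.
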